7.2 Analysis Populations

Final analysis populations will be determined and agreed upon prior to database lock and patient unblinding as described in section 7.3.2.

7.2.1 Screen Failures

Investigators must account for all subjects who sign informed consent and will maintain an Enrollment Log capturing subjects screened and indicating who was enrolled or excluded and the reason why. If the subject is found not to be eligible prior to enrollment, the reason(s) for ineligibility must be documented by the Investigator.

These subjects will neither contribute to data presentations nor be included in formal statistical analyses. The number of screen failures will be included in the data disposition table. Subject Numbers assigned to subjects who fail Screening will not be re-used.

STATISTICAL ANALYSIS PLAN

Version 3.0 12-Jan-22

7.2.2 Subjects Enrolled and Subjects Not Assigned

Subjects are considered enrolled if they sign informed consent and meet all eligibility criteria. Randomization is not a requirement for subjects to be considered enrolled.

Any subject who meets eligibility criteria but is not randomized (e.g., withdrew from the study, lost-to-follow-up, etc.), will be classified as "Not Assigned" in the statistical outputs. This group of subjects will not include Screen Failures as those subjects will be reported separately.

Thus, enrolled subjects consist of randomized subjects and not assigned subjects.

7.2.3 Safety Population

The safety population includes all subjects who apply at least 1 dose of study medication. Subjects will be grouped as treated.

7.2.4 Modified ITT Population

Modified Intent to Treat (mITT): All randomized participants who apply at least 1 dose of study medication and have at least one post-baseline evaluation on-site visit. Subjects will be grouped as randomized.

This is a change from the protocol.

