	Day 14 (Week 2) and Day 28 (Week 4). All subjects will be asked to attend a
	Week 8 follow-up visit 4 weeks (28 days (±3) days) after the last dose of study
	medication.
Statistical Considerations:	Sample Size:
	Approximately 576 subjects may be enrolled to account for 16.7% drop out rate prior to completing the study.
	A total of 160 evaluable subjects per group (480 total) are required to achieve
	at least 80% to detect a pairwise difference of 0.65 in mean WI-NRS change
	from baseline to Week 4 between one of two active doses of B244 and vehicle
	control when assuming a standard deviation of 2.5 and applying a Dunnett

Testing Method at a one-sided familywise error rate of 0.10.

Populations:

- ITT population: All subjects who are enrolled and apply at least 1 dose of study treatment will be included in the Intent to Treat (ITT) population. The ITT population will be the primary population for safety and efficacy assessments.
- Per Protocol (PP) population: All subjects in the ITT population without any protocol deviations that may have an impact on the efficacy assessments, who complete their Week 4 visit, and who administer at least 50% of investigational product (IP), will be included in the Per Protocol (PP) population.
- Safety Population: All subjects treated with at least one dose of IP.

Efficacy Analysis:

Efficacy analysis will be performed on the ITT population with some supportive analysis on the PP population. Regression models will include all eligible subjects for the respective analysis, from the 3 treatment arms.

Hypothesis tests for the primary efficacy endpoint will be performed using a Dunnett Testing Method, applying pairwise comparisons of each respective B244 dose group to vehicle using a one-sided familywise error rate of 0.10. No additional adjustments will be made for multiple testing.

Additional supportive analyses may be performed combining the B244 dose groups in comparison against vehicle and comparison of the B244 groups to one another.

The frequency and rate of NRS responders at Week 4 (≥4 point change from baseline in NRS) will be reported and compared between treatment groups using a logistic regression model.

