12.2 Populations for Analysis

Intent to Treat (ITT): All randomized participants who apply at least 1 dose of study medication. Subjects will be grouped as randomized.

Per Protocol: All subjects in the ITT population without any major protocol deviations that may have an impact on the efficacy assessments, who complete their Week 4 visit, and who administer at least 50% of investigational product (IP). Subjects will be grouped as treated.

Safety: All subjects who apply at least 1 dose of study medication. Subjects will be grouped as treated.

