2.3 Schedule of eDiary and Efficacy Assessments

eDiary (ePRO) is provided to subjects at the screening visit for daily entry at home (e.g., application on smartphone). Questionnaires and clinician assessments are recorded via ePRO/eCOA (e.g., tablet) or CRF during the site visits per schedule of events. Additional patient reported information include rescue medication use, dose administration confirmation, and adjunctive therapy use.

| Device | Assessment | Frequency and Duration of Assessment |
|----------|--|--|
| eDiary | WI-NRS | Once daily from Screening visit through the Follow-up visit |
| eDiary | AI-NRS | Once daily from Screening visit through the Follow-up visit |
| eDiary | Patient Reported Local Tolerability | Once daily from Day 1 to Day 7 of treatment |
| eDiary | POEM | Patient reported at site visits |
| eDiary | 5-D Pruritus Scale | Patient reported at site visits |
| eCOA/CRF | IGA | Clinician assessment at site visits |
| eCOA/CRF | EASI | Clinician assessment at site visits |

STATISTICAL ANALYSIS PLAN

Version 3.0 12-Jan-22

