7.2.6 Role of Populations in Analyses

The results in the mITT population will be considered definitive for superiority of each active treatment to vehicle with those in the PP population considered supportive. Safety analyses will be performed using the Safety population.

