7.7 Changes to Planned Analyses

Protocol: PRB244-01 Confidential STATISTICAL ANALYSIS PLAN

Version 3.0 12-Jan-22

With respect to planned analyses in the protocol, the following changes have been made:

- Use of Modified Intent to Treat (mITT) population rather than Intent to Treat (ITT) population. Both populations consist of subjects who are enrolled and apply at least 1 dose of study treatment. mITT population also requires that at least one post-baseline evaluation visit occur.
- Reporting of endpoints for all visits have been added.
- Responder endpoints for EASI and IGA have been added.
- The protocol states that the treatment period is 28 days, yet the IP administration in the Schedule of Assessments covers a 29-day period (Visit 2 to Visit 4). In order to be consistent with the 28-day treatment period, the time frame of Visit 2 to Visit 4-1 will be used to report the following data:
 - NRS rating scores
 - "On-treatment" rescue medication use
 - Dosing diaries for secondary compliance

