| | | B244 O.D. 5.0 | B244 O.D. 20.0 | Pooled B244 | Vehicle | All Subjects |
|---|-----------|---------------|----------------|-------------|-----------|--------------|
| Number of Subjects | Statistic | | | | | - |
| Enrolled | n | XX | XX | XX | XX | XX |
| Randomized [1] | n (%) | xx (xx.x) | xx (xx.x) | xx (xx.x) | xx (xx.x) | xx (xx.x) |
| Included in Safety (SAF) [2,4] | n (%) | xx (xx.x) | xx (xx.x) | xx (xx.x) | xx (xx.x) | xx (xx.x) |
| Excluded from Safety (SAF) | n (%) | xx (xx.x) | xx (xx.x) | xx (xx.x) | xx (xx.x) | xx (xx.x) |
| No IP Applied | n (%) | xx (xx.x) | xx (xx.x) | xx (xx.x) | xx (xx.x) | xx (xx.x) |
| Included in Modified Intent-to-Treat (mITT) [3,5] | n (%) | xx (xx.x) | xx (xx.x) | xx (xx.x) | xx (xx.x) | xx (xx.x) |
| Excluded from Modified Intent-to-Treat (mITT) | n (%) | xx (xx.x) | xx (xx.x) | xx (xx.x) | xx (xx.x) | xx (xx.x) |
| No Post-Baseline Evaluation Visit | n (%) | xx (xx.x) | xx (xx.x) | xx (xx.x) | xx (xx.x) | xx (xx.x) |
| Included in Per Protocol (PP) [6] | n (%) | xx (xx.x) | xx (xx.x) | xx (xx.x) | xx (xx.x) | xx (xx.x) |
| Excluded from Per Protocol (PP) | n (%) | xx (xx.x) | xx (xx.x) | xx (xx.x) | xx (xx.x) | xx (xx.x) |
| Major Protocol Deviation | n (%) | xx (xx.x) | xx (xx.x) | xx (xx.x) | xx (xx.x) | xx (xx.x) |
| Did Not Complete Week 4 Visit | n (%) | xx (xx.x) | xx (xx.x) | xx (xx.x) | xx (xx.x) | xx (xx.x) |
| Applied < 50% IP | n (%) | xx (xx.x) | xx (xx.x) | xx (xx.x) | xx (xx.x) | xx (xx.x) |

[1] Percentage based on number enrolled.

[2] Percentage based on the number randomized.

[3] Percentage and all subsequent percentages based on the number treated.

[4] Safety Population: All subjects treated with at least 1 dose of IP.

[5] Modified Intent-to-Treat Population: All randomized participants who apply at least 1 dose of IP and have at least one post-baseline evaluation visit.

[6] Per Protocol Population: Includes all subjects in the mITT population who administered at least 50% of IP (based on the weight of IP used calculated using the algorithm:

difference in weight of all bottles dispenced and weight of all bottles returned must be at least 50% of the initial theoretical product weight i.e.(0.14 g per pump x 20 pumps per day x 28 days = 78.4 g)), have completed their Week 4 visit and did not have any major protocol deviations.

Source: Listing XXXX

PROGRAM NAME: XXXXXXXXX

DATE: HH:MM/DDMMMYYYY

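### The SAP's definitive mITT requires a post-baseline on-site visit, a post-randomisation condition that the home-diary endpoints do not need; the protocol's dosed ITT should be definitive

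*SAP*

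**What the plan says.** Protocol 12.2 defines ITT as "All randomized participants who apply at least 1 dose of study medication. Subjects will be grouped as randomized". The protocol synopsis states its role: "The ITT population will be the primary population for safety and efficacy assessments". Protocol 12.5 plans the efficacy analyses on ITT and PP.

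SAP 7.2.4 adds a condition. The mITT is "All randomized participants who apply at least 1 dose of study medication and have at least one post-baseline evaluation on-site visit". The section says openly that this departs from the protocol, and SAP 7.7 lists it: "Use of Modified Intent to Treat (mITT) population rather than Intent to Treat (ITT) population". Neither place gives a reason. SAP 7.2.6 fixes the status of the new population: "The results in the mITT population will be considered definitive for superiority of each active treatment to vehicle".

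The itch scores do not come from visits. SAP 2.3 says "eDiary (ePRO) is provided to subjects at the screening visit for daily entry at home", and under SAP 6.5.3 one daily score is enough for a weekly average.

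The addendum of 22 April 2022 answers an FDA request. It adds an analysis of all randomised subjects, dosed or not, with LOCF at Week 4. It calls this a sensitivity analysis and also labels the population ITT. No planned table therefore uses the protocol's own ITT.

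**The concern.** A population defined by what happens after randomisation can differ between arms for reasons linked to treatment. Whether a subject returns to the clinic can depend on tolerability or lack of effect, so exclusions need not be balanced.

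The protocol's one-dose condition is milder. The first application takes place at the Baseline visit under supervision (Protocol 10.6.3), so that condition should remove very few.

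The visit condition would be easier to defend for IGA, EASI, POEM and 5-D, which are collected on site. For WI-NRS and AI-NRS it discards data that exist. The only scheduled contact between Baseline and the Day 14 visit is a telephone call (Protocol 10.6.4), so a dosed subject can build up about two weeks of valid diary entries and still be outside the definitive population.

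**Working it through.** **1. Membership, side by side**

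- Protocol ITT: randomised and at least one dose.
- SAP mITT: randomised, at least one dose, and at least one on-site evaluation after baseline.
- Addendum ITT: randomised.

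The mITT excludes a dosed subject only if no qualifying visit takes place at Week 2, Week 4, Week 8 or Early Termination. The wording varies. SAP 7.2.4 requires the visit to be on site. SAP 7.7 and the footnotes to Tables 14.1.1.1 and 14.1.1.2 ask only for an evaluation visit, and Table 14.1.1.2 gives the exclusion reason as "No Post-Baseline Evaluation Visit". Nothing says whether an Early Termination visit counts.

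**2. Which analyses lose something**

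- *Primary ANCOVA.* It uses the observed Week 4 average (diary days from Day 22), and SAP 7.6 allows no imputation. A subject who left before Day 14 has no Week 4 value in either population. Only a subject who kept the diary but attended no visit is lost.
- *MMRM (SAP 7.4.1).* A dosed subject with Week 1–2 entries who never returns is lost entirely. Under the protocol's ITT those weeks would enter the model and, through the within-subject covariance, inform later weeks.
- *NRI (SAP 7.4).* A subject who discontinues with a TEAE leading to discontinuation, or who uses rescue medication on treatment, should count as a non-responder from then on. If that subject never returns, the mITT removes the failure from numerator and denominator alike.
- *WOCF (addendum, Request 1).* It is run on mITT, so it has the same gap.

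**3. Size**

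The plan's enrolment figure reproduces: 160/(1 − 1/6) = 192 per group, and 3 × 192 = 576. With the rounded 16.7%, 160/0.833 = 192.1, which rounds up to 193. The allowance for all losses is therefore 192 − 160 = 32 per group. The documents do not say how many of these would have no on-site visit, so what follows is an assumed range.

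*Bias.* Let q be the fraction of an arm excluded, and let excluded subjects improve g points less than retained ones. The mean change over all dosed subjects then differs from the retained mean by q × g, and the treatment difference shifts by g × (q_active − q_vehicle).

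- Gap of 2 percentage points, g = 2: 0.02 × 2 = 0.04 points; 0.04/0.65 = 6% of the design difference.
- Gap of 5 percentage points, g = 3: 0.05 × 3 = 0.15 points; 0.15/0.65 = 23%.
- Equal exclusion rates and equal g in both arms: 0.

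This is the distance from a comparison that counts every dosed subject's outcome. It is not the change expected in the observed-data ANCOVA, where most of those outcomes are missing under either population.

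*Precision.* Pairwise power is Φ(0.65/(2.5 × √(2/n)) − 1.577), where 1.577 is the one-sided Dunnett critical value for two comparisons at familywise 0.10 (correlation 0.5, normal approximation). If every retained subject had Week 4 data, power is 83.4% with none excluded (192 per arm), 81.8% with 5% excluded (182.4) and 79.9% with 10% excluded (172.8). Lost precision is secondary; the concern is selection.

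**The case against.** The strongest defence has four parts. The change is declared, and exclusions are counted by arm in Table 14.1.1.2 and listed in Listing 16.2.3. Subjects who stop treatment early are due a visit within 7 days of the last dose plus a follow-up visit (Protocol 8.9), and the Early Termination visit collects all the efficacy scores (Protocol 10.6.8). The primary ANCOVA hardly depends on the choice. The addendum's population is broader than the protocol's ITT and covers the primary ANCOVA and most responder endpoints at Week 4. A subject with no on-treatment value carries baseline forward there and so counts as a non-responder.

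Much of this stands, and it rules out three readings that a reader might infer:

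- *That early adverse-event dropouts as a group are removed.* Not supported. One qualifying visit is enough, and an Early Termination visit plausibly qualifies.
- *That the NRI response rate is overstated in proportion to the number excluded.* Not supported. SAP 7.4 imputes discontinuation only when a TEAE led to it, rescue use being the other route. The table shells take as denominator the subjects with data at that visit. Those lost to follow-up with neither event stay missing in both populations.
- *That COVID-19 disruption (SAP 7.5.9) implies many exclusions.* Not supported. One missed visit excludes nobody. A diary-only subject reaching Week 4 should be rare, since the third bottle is dispensed at the Week 2 visit and each lasts about 10 days (Protocol 8.6).

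The defence does not justify the visit condition itself. The addendum leaves mITT definitive, works at Week 4 only, and does not extend to the NRI, weekly MMRM or WOCF analyses.

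**Conclusion.** The point holds in a limited form. The SAP makes definitive a population that is conditioned on a post-randomisation clinic visit, gives no reason, and applies it to endpoints recorded at home. The loss falls on the MMRM and NRI analyses, through dosed subjects who never return on site. The direct effect on the Week 4 ANCOVA is probably small.

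The number excluded cannot be derived from the documents. The 0.04 to 0.15 point range rests on assumed exclusion gaps of 2 and 5 percentage points and assumed outcome gaps of 2 and 3 points, and it vanishes if exclusions and outcome gaps are the same in both arms. The addendum reduces the problem without removing it. The unclear status of the Early Termination visit adds to it, because membership of the definitive population is open to interpretation.

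**What to change.** 1. Make the protocol's ITT (randomised, at least one dose, grouped as randomised) the definitive efficacy population for the ANCOVA, MMRM and NRI analyses, and amend SAP 7.2.4, 7.2.6, 7.4 and 7.7 to match.
2. Keep mITT as a sensitivity analysis.
3. Use one wording for the qualifying visit in SAP 7.2.4, SAP 7.7 and the table footnotes, and state whether an Early Termination visit counts.
4. Give the addendum's all-randomised population a different label from the protocol's ITT.

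The cost is SAP wording, table titles and reruns on data already collected. The change supplies no method for missing Week 4 values. SAP 7.6 has none for the primary analysis, and without one the population change alone will move the primary result little.

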7.2.5 Per-Protocol (PP) Population

The PP population includes all subjects in the mITT population without any major protocol deviations that may have an impact on the efficacy assessments, who complete their Week 4 visit, and who administer at least 50% of investigational product (IP). Subjects will be grouped as treated.

7.2.6 Role of Populations in Analyses

The results in the mITT population will be considered definitive for superiority of each active treatment to vehicle with those in the PP population considered supportive. Safety analyses will be performed using the Safety population.

7.3 General Analysis

7.3.1 Subjects Disposition

The subject disposition summary will include the number screened, the number of screen failures, the number enrolled, the number in each patient population for analysis, the number who completed the study, the number who discontinued the study and reason for discontinuation from the study. Disposition data will be summarized by treatment and pooled B244 treatment arm.

STATISTICAL ANALYSIS PLAN

Version 3.0 12-Jan-22

A summary table of analysis populations and reasons for exclusion will be presented for all subjects enrolled.

A by-subject data listing of study completion information including the reason for study discontinuation will be presented. A by-subject listing of inclusion/exclusion criteria not met will also be presented.

7.3.2 Clinical Trial Protocol Deviations

A summary of all major protocol deviations for mITT and Safety populations by category will be generated. Protocol deviation data will be summarized by treatment and pooled B244 treatment arm. A by-subject data listing of all protocol deviations will also be presented. Protocol deviations will be categorized as major or minor per Protocol Deviation Guidance v2.1. At the discretion of the Sponsor, major protocol deviations, as determined by a review of the data prior to unblinding of the study results and the conduct of statistical analyses, may result in the removal of a subject's data from the PP population. Biorasi and its data monitoring group as applicable will be responsible for producing the final protocol deviation and clearly identify whether or not this violation warrants exclusion from the PP population. This file will be finalized prior to hard database lock.

7.3.3 Demographic and Baseline Characteristics

Demographic and Baseline characteristic data summarization will be performed in order to descriptively assess the comparability of treatment groups. Data to be tabulated will include age, race, sex, ethnicity, height, weight, BMI, smoking status, and rescue medication days during the 2-weeks prior to baseline as well as Baseline WI-NRS, AI-NRS, IGA, EASI, BSA, 5-D Pruritus Scale, and POEM scores.

7.4 Efficacy Analysis

All efficacy analyses will be performed on the mITT population and PP population using the methods described below. Regression models will include all eligible subjects for the respective analysis, from the 3 treatment arms.

- *Primary Analysis*: Includes data for all subjects in the respective population (mITT/PP)
- *Sub-Analysis*: Excludes data collected on/after date of first on-treatment rescue medication use through the end of the study.
 - For WI-NRS/AI-NRS endpoints, excludes data from *week* of first on-treatment rescue medication use.
- *Non-Responder Imputation (NRI) Analysis*: Subjects who discontinue treatment early or who take on-treatment rescue medications will be imputed as a non-responder for assessments that occur on/after date of discontinuation/on-treatment rescue medication use through the end of the study.

STATISTICAL ANALYSIS PLAN

Version 3.0 12-Jan-22

- For WI-NRS/AI-NRS endpoints, excludes data from *week* of discontinuation/first on-treatment rescue medication use.
- Subjects who discontinue early should have at least one treatment-emergent adverse event (TEAE) leading to discontinuation in order to have their data imputed for NRI analysis.

| Efficacy Analyses | lyses | A | cacy | Effi |
|-------------------|-------|---|------|------|
|-------------------|-------|---|------|------|

| Measure | Endpoints | Analysis |
|--------------------|---|--|
| WI-NRS/ AI-NRS* | Mean Change from Baseline | Primary Primary/Sensitivity Sub-Analysis Sub-Analysis/Sensitivity |
| WI-NRS/ | Improvement | Primary Primary/Sensitivity Sub-Analysis Sub-Analysis/Sensitivity NRI NRI |
| AI-NKS* | (4-Point, Any) | 6. NRI/Sensitivity |
| 5D | Mean Change from Baseline | 2. Sub-Analysis |
| EASI | Mean Change from Baseline | Primary Sub-Analysis |
| EASI | Improvement (≥50%, ≥75%, ≥90%) | 1. Primary 2. Sub-Analysis 3. NRI |
| IGA | Mean Change from Baseline | 1. Primary 2. Sub-Analysis |
| IGA | Improvement (2-Point to Clear/Almost Clear, Clear/Almost Clear, Any) | Primary Sub-Analysis NRI |
| POEM | Mean Change from Baseline | Primary Sub-Analysis |

*WI-NRS/AI-NRS analyses require at least 1 diary entry per week to calculate the weekly average, except for the sensitivity analyses, where at least 4 diary entries per week are required.

PP population excludes subjects with any major protocol deviation that may impact efficacy and safety analyses, including those with any confounding events or those over the rescue medication use limits but includes data for subjects below rescue medication use limits. Rescue medication

STATISTICAL ANALYSIS PLAN

Version 3.0 12-Jan-22

use below the allowed limit per protocol are considered minor protocol deviations, are considered non-confounding, and is included in the PP population.

The following events are confounding:

- Change in stable use of oral H1 antihistamines (e.g., change in type, dose, and frequency of medication)
- Change in stable use of bland emollients (e.g., change in type, dose, and frequency of treatment)
- Use of excluded medications during study
- Use of rescue medications over the allowed limit per protocol (over 3 rescue medication days during the 2-week washout period, over 7 rescue medication days during the 4-week treatment, and over 7 rescue medication days during the 4-week follow-up)

In the PP sub-analysis, all subject data over the rescue medication limits per the PP primary analysis will be excluded, but subject data below the rescue medication limits will be included up to the date or week that the first rescue medication is taken.

Hypothesis tests for the primary efficacy endpoint will be performed using a Dunnett Testing Method, applying pairwise comparisons of each respective B244 dose group to vehicle using a one-sided familywise error rate of 0.10. Section 7.4.2 provides further details. No additional adjustments will be made for multiple testing. As such, p-values from analysis of secondary and exploratory efficacy analyses must be interpreted in an exploratory fashion.

Supportive analyses may be performed for all efficacy analyses combining the B244 dose groups in comparison against vehicle and comparison of the B244 groups to one another.

Furthermore, stratified analyses will be performed by presenting descriptive statistics by age group, race, gender, IGA at Baseline (2 or 3), EASI at baseline (≤ 10 or >10), BSA range at Baseline (10 to 20%, >20 to 30%, >30 to 40%), rescue treatment used at Baseline (Yes, No), and rescue medication used while on treatment (Yes/No).

In case there are clear differences between groups in the stratified analyses, then post-hoc sensitivity analyses may be performed to control for those covariates in the appropriate statistical model. This post-hoc analysis may also include examination of outcome measures stratified by presence/absence of asthma at Baseline. Site related baseline covariates may also be analyzed post-hoc as described in Section 6.5.12. The effect of seasonality may also be investigated via seasonal pattern as one sine and one cosine function³, if applicable, including interaction with site specific covariate. Post-hoc analysis may also include examination of outcome measures that include/exclude certain lots due to aging or stratified by investigational product lot.

STATISTICAL ANALYSIS PLAN

Version 3.0 12-Jan-22

